If a participant is unable to read, an impartial third party witness will have to be present during the consent process to confirm that the process has taken place. The consent document must be read to the participant and the process documented in the research file. The participant will "make their mark" (f.ex. thumbprint) on the signature section of the consent document, in order to document their understanding. Both the witness and the person obtaining informed consent. Both the witness and the person obtaining informed consent must also sign and date the consent.

RCT Treatment randomization: After obtaining written, informed consent and following all screening and study baseline procedures, individuals in the RCT will be randomized on a 1:1 basis to participate in either TEAM or ETAU. Block randomization with block sizes ranging randomly between 4 and 8 consecutive patients will be employed to ensure that equal numbers of TEAM and ETAU patients occur within strata and are balanced with respect to relevant comorbidity (diabetes and previous stroke). The randomization list will be computer-generated by personnel within the biostatistics core of the CWRU Neurological and Behavioral Outcomes Center who are not members of the study staff.

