Measures: Demographic variables and existing medical burden (assessed with the self-reported Charlson Index⁷⁹) will be evaluated at baseline, prior to study randomization. Baseline medical status will also be evaluated with personal and family stroke history as well as currently prescribed medications. Primary outcome of the RCT will be change in systolic BP from baseline to 6-month follow-up. Additional outcomes of interest will include diastolic BP, cholesterol/lipids and glycosylated hemoglobin (HbA1c) (approximately 5mL of blood is drawn per blood draw), body mass index (BMI), measures that evaluate diet, activity levels, substance use, self-efficacy, stroke knowledge, stress, medication adherence, medication access and health resource use. Quantitative measures will be repeated at 13-week and 24-week (6-month) follow-up except for laboratory testing, which will be conducted only at baseline and 24-week follow-up. Qualitative evaluation will be conducted at baseline and at 13-week follow-up.

[figure not shown]
Primary outcome: The primary study outcome is systolic BP measured at baseline, 13-week, 24-week (6 month). All BP measurements will adhere to a standardized procedure previously used by this study team.³⁰ Prior to BP measurement study participants will be requested beforehand to refrain from smoking and drinking alcohol or caffeinated beverages at least half an hour before the examination. BP will measured with an Omron automated sphygmomanometer model HEM 907 whose accuracy has been validated.⁸⁰ The participant will be asked to sit on a chair and rest quietly for 15 minutes with his/her legs uncrossed. The left arm will then be placed on a table with the palm facing upward and the ante-cubital fossa at the level of the lower sternum. Two arm cuffs that fitted arm circumferences 9-13 inches and 13-17 inches will be available for use in BP measurement. Three measurements will be taken at least 5 minutes apart. The average of the last two readings will be considered as the final blood pressure reading.

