Quantitative data Analysis: Preliminary descriptive analyses will examine change over time in systolic BP as well as secondary outcomes. The measures of interest are valid and reliable, and have been used in stroke studies in the SSA setting.^{24, 30, 88, 97, 98} Primary and secondary outcome measurements will be assessed at baseline prior to randomization to either TEAM or ETAU, and at the 13 week and 6 month time-points using the same methods as in our pilot work. Of primary interest is the treatment by time interaction in systolic BP, measured from baseline to 6 months after randomization between TEAM and ETAU. Explanatory variables will include age, gender, stroke history and rural vs. urban status.

The 13-week systolic BP measurement will reflect the period following baseline (when individuals participating in TEAM Uganda will have just completed the “intensive” group sessions), and it will be used to assess for within-subject differences from baseline to 13 weeks and 13 week to 6-month time periods. This will allow for a greater understanding of the time course for when the expected reductions occur in the TEAM Uganda group, which we expect to mostly occur after the “intensive” group sessions have ended. We will analyze change from baseline to 13 weeks as well, analyzing contrasts within the mixed model framework.

For aim 2, we will use 2 group by 3 time waves repeated measures analysis of variance (RMANOVA) for each of the 3 hypotheses in Aims 2. These analyses will compare two groups (TEAM intervention vs. enhanced treatment as usual (ETAU)) across three time waves of systolic BP (H1), serum cholesterol (H2), and serum HbA1c (H3). When using a repeated measures ANOVA, it not only assesses mean differences across time, but also assesses group differences, as well as, the interaction of time X group which will allow us to test the trend of the means over time across the three groups. The repeated measures ANOVA, not only can be used to determine if there are mean differences across the three time periods, it can also utilize orthogonal polynomial contrasts to determine linear and quadratic trends of the means across time. Orthogonal polynomials are weights

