Sample size calculations: From our pilot data, mean baseline systolic BP was 162.9 (SD 25.6). Change from baseline to 6 months with the TEAM Uganda intervention saw a mean systolic BP of 149.7 (SD 22.1). Reductions BP of ≥ 2 mm Hg can significantly reduce the incidence of cardiovascular disease and its complications in both hypertensive and normotensive individuals, and reductions of the magnitude seen in this team's pilot work is well above thresholds that are considered clinically meaningful.^{94, 95} Our projected sample size is n=246, with 123 participants per arm. Based on our preliminary mixed model, we observed difference in systolic BP from baseline to 24 weeks of 13.22, with standard deviation of 25.84, and within subject correlation parameter value of 0.57. However, we will conservatively estimate our sample size based upon a difference of 10 mmHg, commensurate with a meta-analysis that used this magnitude of change in BP across a large sample with varying baseline blood pressure levels and comorbidities.⁹⁶ Also in our pilot work with the TEAM Uganda study, we observed an attrition rate of 12.5% at 6-months follow-up. Conservatively, for this study, we will assume 25% attrition. Finally, to assume for two-sided test of time-by-treatment group interaction, Type I error level is 0.05. Then, in a linear mixed model with subject-level and center-level random effects, power is 0.80 for a clinically significant difference of 10.0 mm Hg between treatment arms for the projected sample size of 246 subjects in total. We should thus have sufficient power. We do assume compound symmetry over the 3 time periods. We will also consider an AR(1) covariance model, and compare model fits.

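### The planned 24-week systolic BP contrast leaves baseline free to differ by arm; adjusting for or constraining baseline would cut its variance by about 21% (scenarios 17% to 34%) with no new data

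*Combined protocol and SAP*

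**What the plan says.** The primary test, in the Data Analysis Plan under Quantitative data Analysis, reads: "Of primary interest is the treatment by time interaction in systolic BP, measured from baseline to 6 months after randomization". For each Aim 2 hypothesis the same section specifies a two-group, three-wave repeated measures ANOVA (RMANOVA), with baseline as the first wave.

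It also says that outcomes are "assessed at baseline prior to randomization to either TEAM or ETAU". The RCT Treatment randomization paragraph agrees, placing allocation after all baseline procedures.

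On covariates it says: "Explanatory variables will include age, gender, stroke history and rural vs. urban status". Baseline systolic BP is not listed, and nothing in the document sets the baseline means equal across arms.

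The Sample size calculations section uses a "standard deviation of 25.84, and within subject correlation parameter value of 0.57". It assumes compound symmetry, a 10 mmHg difference, two-sided alpha 0.05, 25% attrition and 246 participants, and states power of 0.80 "in a linear mixed model with subject-level and center-level random effects".

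Two further statements bear on the model:
- Allocation is balanced on diabetes and previous stroke, but only stroke history is among the explanatory variables.
- The RMANOVA description has no site term, although the power statement has a centre-level random effect.

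**The concern.** When baseline is an outcome wave with a free mean in each arm, the baseline-to-24-week interaction subtracts the observed baseline difference between arms in full. Randomisation makes the expected value of that difference zero, so subtracting all of it adds noise. A baseline-adjusted or baseline-constrained model subtracts only the share that the correlation supports. The loss comes from leaving the baseline difference free, not from keeping baseline in the model.

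The listed covariates do not make up for this, because an effect that is constant over time cancels from a change score. The same holds for diabetes and centre. They affect precision only if they predict change in systolic BP or once the model is baseline-adjusted, and the documents give no figure for either.

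At stake is precision on the primary outcome. Bias is not at issue.

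**Working it through.** **Inputs (Sample size calculations).** SD 25.84, read as the SD at one visit; correlation rho = 0.57; difference 10 mmHg; 123 per arm; 25% attrition, so about 92 completers per arm; two-sided alpha 0.05. Pilot SDs are 25.6 at baseline and 22.1 at 6 months. Clustering, centre effects and the listed covariates are left out.

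**Step 1: reproduce the stated power.**
- SD of change = 25.84 × √(2 × (1 − 0.57)) = 23.96.
- SE = 23.96 × √(2/92) = 3.533.
- t-based power for 10 mmHg = 0.804, against 0.80 stated.
- Required n = 91 per arm; 91/0.75 rounds up to 122, or 244 in total, against 246 stated.

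The trial is therefore sized on the unadjusted change-score variance. If 25.84 is read instead as the SD of the change, power at 92 per arm is only 0.74, which does not reproduce the plan.

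**Step 2: adjust for baseline (completers, compound symmetry).**
- Residual SD = 25.84 × √(1 − 0.57²) = 21.23; SE = 21.23 × √(2/92) = 3.130.
- Variance ratio = (1 − rho²) / (2(1 − rho)) = (1 + rho)/2 = 0.785, a reduction of (1 − rho)/2 = 21.5%.

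**Step 3: keep dropouts' earlier data.** I used generalised least squares on three waves, with 123 per arm of whom 31 lack the 24-week value, and compared free with equal baseline means.

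**Step 4: pilot SDs (completers, rho 0.57).**
- Variance of change = 25.6² + 22.1² − 2 × 0.57 × 25.6 × 22.1 = 498.8.
- Adjusted variance = 22.1² × (1 − 0.57²) = 329.7; ratio 0.661.

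| Scenario | SE, planned → adjusted | Variance reduction | Power for 10 mmHg | 95% CI half-width (mmHg) |
|---|---|---|---|---|
| Completers, compound symmetry | 3.533 → 3.130 | 21.5% | 0.804 → 0.888 | 6.97 → 6.18 |
| Dropouts kept, all lost before week 13 | 3.436 → 3.130 | 17.0% | 0.825 → 0.888 | 6.78 → 6.18 |
| Dropouts kept, all lost after week 13 | 3.388 → 3.078 | 17.5% | 0.835 → 0.898 | 6.69 → 6.07 |
| Completers, pilot SDs | 3.293 → 2.677 | 33.9% | 0.856 → 0.960 | 6.50 → 5.28 |

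**Step 5: the AR(1) alternative.** The plan says AR(1) will also be considered. If 0.57 is the lag-one correlation (an assumption), the baseline-to-24-week correlation is 0.57² = 0.325. The reduction in completers is (1 − 0.325)/2 = 33.8%, and power goes from 0.61 to 0.79.

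**Step 6: equivalent enrolment.** To match the adjusted precision, the planned contrast would need 246/0.785 = 313 participants (246/0.83 = 296 to 246/0.661 = 372).

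**Limit.** These figures concern the single-degree-of-freedom 24-week contrast. The two-degree-of-freedom group-by-time test, with 92 per arm and 10 mmHg at 24 weeks, has power 0.714 if the 13-week effect is 5 mmHg and 0.838 if it is 0 or 10 mmHg. The gain from adjustment was not worked out for that test.

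**The case against.** The strongest reply is that nothing is broken. The planned contrast is unbiased and reaches its stated power, and 25% attrition is twice the pilot's 12.5%. At 12.5% attrition, about 107 completers per arm, the unadjusted contrast already has power of about 0.86. This stands, and it is why the point is one of efficiency.

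Other points stand in part:

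- **Which model.** The 21.5% belongs to complete-case RMANOVA, which the plan names for Aim 2. The power and missing-data text points to a mixed model, for which 17.0% to 17.5% is the fairer figure.
- **The range is not a bound.** With dropouts kept under compound symmetry, an assumed rho of 0.70 gives about 12% and 0.40 about 24%. AR(1) combined with the pilot SDs gives about 44% in completers. With dropouts kept, AR(1) or the pilot SDs alone give about 28% to 29%.
- **The SD.** The sentence giving 25.84 can be read as the SD of the change. Power would then go from 0.74 to 0.84. The percentage reduction under compound symmetry is unchanged.
- **Clustering.** TEAM is delivered in groups of 6 to 8. Clustering would lower both power figures, but the plan's own 0.80 reproduces without it.
- **Covariates.** The explanatory list may not be a complete adjustment set, and the Measures section already names change in systolic BP to 6 months as primary. Even so, no passage adjusts for baseline or constrains it.

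None of these removes the gain or changes the remedy.

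**Conclusion.** The concern holds. The primary contrast leaves the baseline difference free although baseline precedes randomisation, and the plan nowhere uses baseline systolic BP to recover the precision lost. On the plan's own inputs the variance could fall by 21.5% in completers, or by about 17% if a mixed model keeps partial data. It could fall by about 34% with the pilot SDs or AR(1) in completers. These figures rest on a per-visit SD of 25.84, rho of 0.57, 25% attrition and independent participants, and they apply to the 24-week contrast only.

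The plan is valid as written, but it should be changed. It has little margin: the 0.80 depends on compound symmetry with rho 0.57, and a lower correlation reduces planned power while making adjustment more valuable. The diabetes and centre points are smaller inconsistencies whose effect on precision cannot be quantified from the documents.

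**What to change.** 1. Name the between-arm difference in systolic BP at 24 weeks as the primary contrast. Estimate it with baseline systolic BP as a covariate, or with a longitudinal model whose baseline means are equal across arms.
2. Treat the secondary outcomes in the same way. Cholesterol and HbA1c follow the full measurement schedule "except for laboratory testing, which will be conducted only at baseline and 24-week follow-up", so for them this is a baseline-adjusted comparison at 24 weeks and not a three-wave analysis.
3. Add diabetes to the covariates alongside stroke history, except for H3, which is confined to people with diabetes.
4. Reconcile Quantitative data Analysis with Sample size calculations, so that one stated primary model carries a centre term.

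The cost is a revised analysis section. The constrained option replaces the RMANOVA with a different model, but neither option needs new data. The model must be fixed before any unblinded outcome comparison, including the interim analysis planned in the DSMB section once half the participants have completed 6 months. The documents do not say whether that interim has taken place. If it has, keep the planned contrast as primary and report the baseline-adjusted model as supportive.

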assigned to each time period that model a linear or quadratic (non-linear) trend. Repeated measures ANOVA can determine if these trends in the means are significant. A linear trend is indicated if there is a steady increase or decline in scores from the first time wave to the third time wave. A quadratic trend is indicated if there is a change in direction based on scores across the time waves. For example, if there is a decrease in mean scores from T1 (baseline) to T2 (13 weeks), but an increase in scores at the T3 (6 months), this would be indicative of a U trend for the three time periods and a return toward the mean score from T1 to T3. A quadratic trend can also indicate a single change in direction in the trend of the means, for example, if there is a decline in means scores from T1 to T2, and the decreased mean score is maintained at T3. The major assumption to be tested with repeated measures ANOVA is sphericity. Sphericity is a form of compound symmetry and refers to the equality of variances of the differences between each time wave.⁹⁹ If the assumption of sphericity is violated based on the Mauchly's test, SPSS provides an adjusted F, df, and p-value in repeated measures ANOVA to account for this violation. We may also explore repeated measures mixed model approaches to analyze change from baseline to 13 weeks as well, analyzing contrasts within the mixed model framework.

Secondary outcomes: We will model secondary outcomes over time in a similar manner. We will consider generalized linear models when distributions of outcomes are not approximately normally distributed, or transformations of outcome variables to normality. We will also conduct exploratory moderator analyses of the explanatory variables in the primary mixed model. Mediation analyses also will be explored. Potential mediators include dose of TEAM session exposure, medication prescription/access and adherence to a heart healthy diet. Variables with (change) values that appear to be associated with change in systolic BP levels and that appear to differ by treatment will be considered further as mediator variables, following as in MacKinnon (2008)¹⁰⁰ and Preacher and Hayes (2008).¹⁰¹ This will involve single mediator analyses as well as multiple mediator models. These analyses will involve the treatment variable and change in systolic BP values. Associated standard errors of estimated indirect effects will be derived through bootstrapping, using the M-Plus software.

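### The plan names two different analyses for the primary blood-pressure hypothesis without ranking them, and its three-wave test for cholesterol and HbA1c does not fit a two-draw laboratory schedule

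*Combined protocol and SAP*

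**What the plan says.** The target for H1 is clear. Under Measures: "Primary outcome of the RCT will be change in systolic BP from baseline to 6-month follow-up". Under Quantitative data Analysis: "Of primary interest is the treatment by time interaction in systolic BP, measured from baseline to 6 months".

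The method is not. For Aim 2, Quantitative data Analysis says "we will use 2 group by 3 time waves repeated measures analysis of variance (RMANOVA) for each of the 3 hypotheses in Aims 2", lists systolic BP, serum cholesterol and HbA1c as the three outcomes, and describes linear and quadratic trends. If Mauchly's test rejects sphericity, "SPSS provides an adjusted F, df, and p-value in repeated measures ANOVA to account for this violation". Under Secondary outcomes the plan then says: "We will also conduct exploratory moderator analyses of the explanatory variables in the primary mixed model". Sample size calculations uses the mixed model: "in a linear mixed model with subject-level and center-level random effects, power is 0.80". That section assumes compound symmetry and adds: "We will also consider an AR(1) covariance model, and compare model fits".

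Missing Data says that the proposed models are unbiased when data are missing at random, on condition that covariates related to missingness enter the mixed model. It commits to pattern-mixture sensitivity analyses and says that full information maximum likelihood will be considered.

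On laboratory timing, Quantitative data Analysis has primary and secondary outcomes assessed at baseline, 13 weeks and 6 months. Measures exempts laboratory tests from the 13-week visit, and Risks to Research Participants gives two blood draws, at baseline and 6 months.

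**The concern.** Two analyses each have a claim to be the primary test of H1, and no sentence chooses. They can differ in who is included, in degrees of freedom and in what is assumed about missing data. An unranked pair allows the choice to be made after results are known, and a reader of the final report could not tell whether the planned test had been used.

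The missing-data statement makes the choice matter more, because it is worded for all proposed models and one of them, run in the usual way, does not have the property claimed.

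For H2 and H3 the problem is simpler: the test as written needs a 13-week laboratory value that the schedule does not provide.

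**Working it through.** **Inputs** (Sample size calculations): SD 25.84, within-subject correlation 0.57, compound symmetry, difference 10 mmHg, two-sided 0.05, 25% attrition, 123 per arm. Reading 25.84 as the SD at one visit is an assumption, tested in step 1.

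**1. The plan's own figure.** SD of change = 25.84 × √(2 × (1 − 0.57)) = 23.96. The smallest n per arm giving power 0.80 (noncentral t) is 92, with SE = 23.96 × √(2/92) = 3.53 and power 0.804. Allowing for attrition, 92/0.75 = 122.7, so 123 per arm and N=246. Reading 25.84 instead as the SD of change gives N=280 (normal formula), which does not match. The sample size therefore corresponds to the 1-df baseline-to-6-month contrast.

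**2. The same contrast in the mixed model.** With 92 complete participants and 31 dropouts per arm, generalised least squares gives SE 3.39 (power 0.84) if dropouts leave after week 13 and SE 3.44 (power 0.83) if they leave before it.

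**3. The 2-df RMANOVA interaction, 92 completers per arm.** Noncentrality = (92/2) × Σ(d_t − mean d)² / (25.84² × 0.43), where d_t is the arm difference at each wave. The denominator is 287.1; df are 2 and 364. The week-13 difference is not in the documents, so a range is shown.

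| Difference at baseline, week 13, month 6 (mmHg) | Σ(d_t − mean d)² | Noncentrality | Power |
|---|---|---|---|
| 0, 0, 10 | 66.7 | 10.68 | 0.84 |
| 0, 2, 10 | 56.0 | 8.97 | 0.77 |
| 0, 5, 10 | 50.0 | 8.01 | 0.71 |
| 0, 10, 10 | 66.7 | 10.68 | 0.84 |

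**4. How often the choice changes the verdict.** These are simulations with a true 10 mmHg effect and random dropout after week 13 (10,000 trials per pattern). The completer and mixed-model versions of the 1-df contrast disagreed in 6.5% to 7.0% of trials. The 2-df and 1-df tests in the same completers disagreed in 10.8% to 12.1%. Each test alone held about 5% under the null.

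**5. Missing data.** Exclusion of anyone missing a wave is how a conventional RMANOVA runs; it is an inference from the software, not text in the plan. The documents give no dropout mechanism, so the following is illustrative. With a true effect of −10 mmHg, 25% dropout and dropout driven by baseline BP or early response in one arm only, the completer estimate was −7.5 to −12.5. With opposite mechanisms in the two arms it ranged from −5.2 to −15.1. Likelihood-type estimates stayed within about 0.1 of −10. When mechanism and rate were the same in both arms, the completer estimate was also about −10.

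**6. Laboratory outcomes.** Three waves are specified and two are collected. A literal three-wave complete-case analysis has no complete cases. With two waves the interaction has 1 df, there is no quadratic trend, and sphericity has nothing to test. Table 1 is not relied on, because its layout is broken in the text available.

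**The case against.** **A reader might infer that no method is assigned to H1.** One is: the RMANOVA sentence covers all three hypotheses. The fault is a conflict with later sections, not silence. Nor does "We may also explore repeated measures mixed model approaches to analyze change from baseline to 13 weeks as well" show that the mixed model is optional for H1, since it concerns change to 13 weeks.

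**The stated target already excludes the 2-df F.** This has force. The quantity of interest is baseline-to-6-month change, and with waves treated as equally spaced the RMANOVA linear contrast is exactly that 1-df contrast, in completers. The 0.71 applies only if the omnibus interaction is used. What stands is that the plan does not tie its target to the omnibus F, the linear trend or a mixed-model contrast.

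**The missing-data sentence was probably meant for the mixed model.** It mentions that model, and the pattern-mixture commitment is firm. But its subject is all proposed models, so its scope should be stated. A reader might infer that the primary result will be biased; nothing in the documents supports that.

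**A reader might infer that choosing between compound symmetry and AR(1) by fit inflates type I error.** Error rates for one structure imposed regardless of fit do not evaluate that rule. Simulating the rule itself, with adjacent correlation 0.57 and baseline-to-6-month correlation 0.57, 0.50, 0.45 or 0.40 (assumed), gave 5.5%, 5.2%, 5.5% and 4.4% (4,000 null trials each, Monte Carlo error about 0.35 points). A separate simulation gave about 5% to 6%. No material inflation is shown.

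**H2 and H3 are secondary, and a two-wave version is easy to derive.** True, but the plan should state it.

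**Conclusion.** The concern holds as a conflict that the plan leaves unresolved. The RMANOVA is assigned to H1, a mixed model is called primary, and a mixed model supplies the power. The sample size is not in error: N=246 agrees with the 1-df contrast, given the per-visit reading of the SD. The cost of ambiguity is power anywhere from about 0.71 to 0.84 if the omnibus F were used, against 0.80 for the completer contrast and 0.83 to 0.84 for the mixed-model contrast, plus a missing-data claim that does not extend to a completers-only analysis. Bias from that source is conditional on dropout differing by arm, and its size is set by assumption. For H2 and H3 the contradiction is direct and needs no assumption: on the stated laboratory schedule the three-wave test, its quadratic trend and Mauchly's test cannot be run.

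**What to change.** 1. Name one H1 analysis: a likelihood-based linear mixed model on all randomised participants with any systolic BP value, with arm by categorical visit and the center effect from Sample size calculations. State that its 1-df baseline-to-6-month arm contrast decides H1, and which covariates, if any, enter the model.
2. Delete the RMANOVA for H1, or label it a complete-case sensitivity analysis.
3. Limit the missing-at-random statement to the mixed model, and keep the pattern-mixture analyses.
4. For H2, and for H3 in participants with diabetes, replace the three-wave RMANOVA with a two-wave (baseline, 24-week) arm-by-visit analysis. Correct the 13-week assessment statement for laboratory outcomes.
5. Optionally, fix the covariance structure in advance, for example unstructured. This is good practice rather than a correction of a demonstrated error.

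The cost is a wording change. The mixed model already underlies the power calculation, N=246 stands, and no visit or blood draw is added.
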